8.2.3 Further Information for CT/MRI Scans

CT scans, including brain CT scan if applicable, should be performed with contrast agents unless contra-indicated for medical reasons. If IV contrast is medically contra-indicated, the imaging modality to be used to follow the disease (either CT without contrast or MRI) should be the modality which best evaluates the disease, and the choice should be determined by the Investigator in conjunction with the local radiologist. MRI of the abdomen and pelvis can be substituted for CT if MRI adequately depicts the disease. However, MRI of the chest should not be substituted for CT of chest even if IV contrast is contra-indicated. In such cases, CT will be performed without contrast. If MRI is used to follow-up bone lesion(s), it must be performed a few days before any treatment that may affect bone-marrow cellularity (e.g. G-CSF).

The same method and technique should be used to characterize each lesion identified and reported at Baseline, during the study treatment phase, and during follow-up. The use of plainfilm X-rays (with the exception of bone X-rays) is discouraged. The use of positron emission tomography (PET) imaging as the only imaging modality is not permitted.

For patients having effusions or ascites, cases having cytological proof of malignancy should be recorded as non-target lesions on the tumor assessment eCRFs. Effusions that have not been evaluated using cytology or were found to be non-malignant should not be recorded on the non-target lesion CRF.

8.3 Efficacy Parameters

The evaluation of disease response will be conducted according to RECIST v1.1 guidelines.

Protocol No.: POL6326-009

Version 3.0

8.3.1 Progression Free Survival

The primary efficacy variable for this study is time to PFS, based on an assessment by the IRC. A supportive analysis of PFS will be performed based on the local Investigator's review.

PFS is defined as the time from the date of randomization to the earliest evidence of documented PD or death from any cause.

8.3.2 Overall Survival

OS is defined as the time from date of randomization in this study to date of death due to any cause. Patients without a death date will be censored at the date the patient was last known to be alive.

The Investigator will monitor the patient for OS status, for the remainder of the study period, as described in Section 7.

8.3.3 Objective Response Rate

ORR is defined as the proportion of patients with a confirmed CR + confirmed PR. The ORR will be assessed according to RECIST v1.1 guidelines by the IRC and by the local Investigator's review and will be based on the best response assessed.

8.3.4 Time to Response

Time to response is defined as the time from date of randomization to the time of first documented CR or PR as assessed by the IRC and by the local Investigator's review.

8.3.5 Duration of Response

Duration of response is defined as the time from first documented CR or PR until the earliest evidence of disease progression or death from any cause based on the IRC review and the local Investigator's review.

8.3.6 Clinical Benefit Rate

CBR is defined as the proportion of patients with confirmed CR, confirmed PR, or SD for ≥6 months. The CBR will be assessed according to RECIST v1.1 guidelines by the IRC and by the local Investigator's review. CBR will be compared between the treatment arms using logistic regression as described for ORR. Exact Clopper Pearson 2-sided 95% confidence limits will be calculated for the CBR of each treatment arm.

8.3.7 Disease Control Rate

DCR is defined as the number of patients with confirmed CR, confirmed PR, or SD. The DCR will be assessed according to RECIST v1.1 guidelines by the IRC and by the local Investigator's review.

9. ASSESSMENT OF SAFETY

9.1 Safety Assessments

Safety assessments will consist of monitoring all AEs, including SAEs (Section 9.2), regular monitoring of hematology, serum chemistry (Section 9.9), renal function, liver function, ECGs

Protocol No.: POL6326-009

Version 3.0

(Section 9.8), physical examinations (Section 9.6), vital signs (Section 9.7), and ECOG performance status (Section 9.6).

Comprehensive assessment of any apparent AE experienced by the patient will be performed throughout the course of the study, from the time that the patient receives the first dose of study medication until 30 days after the last study drug administration; SAEs will be recorded from the date that the ICF is signed.

Study site personnel will report any AE, whether observed by the Investigator or reported by the patient.

AE assessment will include type, incidence, severity (graded by National Cancer Institute Common Terminology Criteria for Adverse Events [NCI CTCAE] version 5.0, see Section 9.2.3, Severity Assessment), timing, seriousness, and relatedness.

Adverse Events of Particular Interest and Adverse Events of Special Interest

AEPIs include all events of special interest and additionally, all events for which a separate analysis will be performed (Table 9).

AEPIs are based on the emerging AE profile of balixafortide or on the established risks associated with eribulin.

All grade events of thrombocytopenia, peripheral neuropathy, hepatic impairment and QTc interval prolongation have been identified as AEPIs.

Serious events of IRRs, neutropenia and infection, and all cases of renal impairment will be considered AESIs, as well as being AEPIs.

AESIs are to be reported by the Investigator to the Sponsor within **24 hours** of learning of the event.

AESIs must be reported using the same form as for SAEs and notified to the Sponsor within **24 hours** of the Investigator becoming aware of the event, irrespective of causality with the study drug.

Protocol No.: POL6326-009

Version 3.0

Table 9 AEs of Particular Interest and AEs of Special Interest

Adverse Events of Particular Interest	Definition
Thrombocytopenia	Defined using SMQ "Haematopoietic Thrombocytopenia narrow". SMQ code 20000031
Peripheral neuropathy	Defined using SMQ "Peripheral neuropathy narrow" SMQ code 20000034
Hepatic impairment	Defined using SMQ "Liver related investigations, signs and symptoms (SMQ) narrow" SMQ code 20000008
QTc prolongation	Defined using SMQ "Torsade de pointes/QT prolongation "SMQ code 20000001
Hypersensitivity/IRRs	IRRs are defined as AEs that are deemed related to any study treatment by the Investigator, which occurred during infusion or within 24 hours from the end of infusion. Note: IRRs encompass AEs reported as the MedDRA PT "Infusion related reaction" (within the SOC "Injury, Poisoning and Procedural Complications") together with reported signs and symptoms of IRRs
Neutropenia (serious)	Based on reported AEs rather than laboratory values. Defined using SMQ "Haematopoietic Cytopenia" SMQ code 20000027
Neutropenic infections	Defined by PT neutropenic infection
Febrile neutropenia	Defined by the PT febrile neutropenia
Renal impairment	Defined using SMQ "Acute renal failure" SMQ code 20000003
Adverse Event of Special Interest	Definition
Hypersensitivity/IRRs (serious)	IRRs are defined as AEs that are deemed related to any study treatment by the Investigator, which occurred during infusion or within 24 hours from the end of infusion. Note: IRRs encompass AEs reported as the MedDRA PT "Infusion related reaction" (within the SOC "Injury, Poisoning and Procedural Complications") together with reported signs and symptoms of IRRs
Neutropenia (serious)	Based on reported AEs rather than laboratory values
Neutropenic infections	Defined by PT neutropenic infection
Febrile neutropenia	Defined by the PT febrile neutropenia
Renal impairment	Defined using SMQ "Acute renal failure" SMQ code 20000003

AE: adverse event; IRR: infusion-related reaction; MedDRA: Medical Dictionary for Regulatory Activities; PT: preferred term; QTc: corrected QT interval; SMQ: Standardized MedDRA query; SOC: system order class.

Baseline tumor-related signs and symptoms will be recorded at the Cycle 1, Day 1 visit and then reported as AEs (Section 9.2.5) during the study if they worsen in severity or increase in frequency.

Protocol No.: POL6326-009

Version 3.0

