2.6 Balixafortide Current Benefit/Risk Ratio

Balixafortide is being developed in combination with eribulin for the treatment of HER2 negative, locally recurrent metastatic BC, in adult patients who have progressed after at least one chemotherapeutic regimen for advanced disease. Prior therapy should have included an anthracycline and a taxane unless contra-indicated for safety reasons. In this protocol, locally recurrent BC is defined as unresectable locoregionally recurrent BC.

The safety profile of balixafortide is derived from 6 clinical studies (three Phase 1, one Phase 1/2 and two Phase 2 studies) that enrolled a total of 330 subjects, of which 235 subjects received at least one dose of balixafortide, either as a single agent or in combination with other drugs (44). The IV formulation was investigated in a broad range of doses from 0.01–5.5 mg/kg, with IV infusion times between 1 and 3 hours, and treatment duration up to 16 months. The accumulated safety data for balixafortide and the known safety profile of eribulin indicates that the following AEs of special interest (AESIs) should be evaluated and managed in accordance with established guidelines (e.g. American Society of Clinical Oncology [ASCO] guidelines for minimizing the incidence of febrile neutropenia): hypersensitivity/infusion-related reaction (IRRs), neutropenia, febrile neutropenia, infections associated with neutropenia, and renal impairment. The following AEs of particular interest (AEPIs) should be evaluated and managed: thrombocytopenia, QTc interval prolongation, peripheral neuropathy and hepatic impairment. Detailed information is provided in this protocol and the accompanying Investigator's Brochure.

In the Phase 1 study POL6326-007 (Section 2.5.1), the combination of balixafortide + eribulin demonstrated encouraging signs of activity in patients with HER2 negative metastatic BC, and the results showed that the safety and tolerability of balixafortide + eribulin was similar to that of eribulin or balixafortide monotherapy (41). This supports a positive benefit-risk balance in the target population, which is designed to reasonably reflect the target population in clinical practice.

Protocol No.: POL6326-009

Version 3.0

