9.2 Adverse Events

All observed or volunteered AEs regardless of treatment group or suspected causal relationship to the study drug(s) must be reported as described in the following sections.

For all AEs, the Investigator must pursue and obtain information adequate both to determine the outcome of the AE, and to assess whether it meets the criteria for classification as a SAE requiring immediate notification to the Sponsor. Where possible, a diagnosis rather than a list of symptoms should be recorded. If a diagnosis has not been made, then each symptom should be listed individually. For all AEs, sufficient information should be obtained by the Investigator to determine the causality of the AE. The Investigator is required to assess causality. Follow-up by the Investigator may be required until the event or its sequelae resolve or stabilize at a level acceptable to the Investigator, and the Sponsor concurs with that assessment.

If a patient opts to discontinue from the treatment phase because of an unacceptable AE, "Withdrawal of Consent" must not be the reason for discontinuation, rather, the reason for discontinuation must be recorded as "Unacceptable Toxicity". Details of the AE leading to the patient's withdrawal of consent and the action taken must be completed on the AE CRF. AEs must be reported in accordance with the reporting requirements defined in Section 9.2.5.

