9.1.8. Adverse Events of Special and Adverse Events of Particular Interest

Adverse Events of Special Interest (AESI) and Adverse Events of Particular Interest (AEPI) will be identified by the investigator and specified in the eCRF.

The list of AESI is: Hypersensitivity or IRRs (serious), Neutropenia (serious), Neutropenic infections, Febrile neutropenia, Renal impairment.

The list of AEPI is: Thrombocytopenia, Peripheral neuropathy, Hepatic impairment, QTc prolongation, Hypersensitivity/IRRs, Neutropenia (serious), Neutropenic infections, Febrile neutropenia and Renal impairment.

The number and percent of patients reporting an AESI or an AEPI will be summarized by treatment arm, MedDRA SOC and Preferred term. All AESI categories will be summarized, while only the following categories will be summarized for AEPI: Hypersensitivity/IRRs, Thrombocytopenia, QTc prolongation, Peripheral neuropathy and Hepatic impairment.

Number of patients reporting at least one event of Hypersensitivity/IRR, Neutropenia (serious) or Febrile neutropenia will also be summarized by maximum severity (Grade 1 to 5) and treatment arm.

The number of patients reporting Neutropenic infections will be summarized by treatment arm and maximum severity (Grade 1 to 5). This table will only be populated when at minimum 4 patients reported at least 1 event of Neutropenic infection and the number of such patients is more than 1% of the Safety population.

The number of Colony Stimulating Factor (CSP) medications will be summarized for all patients experiencing Neutropenia events.

The number of Hypersensitivity/IRRs and Neutropenia (serious) will be summarized by cycle, day of onset, in total and split by treatment arm. The number of all Hypersensitivity/IRR will also be summarized in terms of the event intensity allowing for multiple reactions within a patient total; the latter will be achieved by means of a Negative Binomial analysis with a fixed effect term for randomized treatment and time exposed to randomized treatment as the offset. The rate ratio and the corresponding 95% confidence interval will be obtained based on the Wald approach using the log as link function.

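### Table 9 defines serious neutropenia two ways and neutropenic infection by one preferred term; the SAP replaces both with an unlinked investigator flag and adds a minimum-count rule

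*Protocol*

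**What the plan says.** Protocol section 2.6 lists the AESIs and includes "infections associated with neutropenia". The text of section 9.1 words the scope differently: "Serious events of IRRs, neutropenia and infection, and all cases of renal impairment will be considered AESIs". AESIs go to the sponsor within 24 hours.

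Table 9 then gives operational definitions in two halves.

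- Serious neutropenia, AEPI half: reported events, with the query "Defined using SMQ 'Haematopoietic Cytopenia' SMQ code 20000027". No narrow or broad scope is stated.
- Serious neutropenia, AESI half: "Based on reported AEs rather than laboratory values", and no query or term list.
- Neutropenic infections, both halves: "Defined by PT neutropenic infection".
- Febrile neutropenia, both halves, as a separate category: "Defined by the PT febrile neutropenia".

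On recording, section 9.2 says: "Where possible, a diagnosis rather than a list of symptoms should be recorded".

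SAP section 9.1.8 has the investigator identify AESIs and AEPIs in the eCRF and plans no query or term search. It summarizes every AESI category, but only five AEPI categories, and neutropenia is not among those five. For neutropenic infections by maximum severity it adds: "This table will only be populated when at minimum 4 patients reported at least 1 event of Neutropenic infection", and a second condition that these patients exceed 1% of the Safety population. SAP section 12, which lists how this plan departs from earlier documents, says all AESIs are summarized by toxicity grade and names no minimum.

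**The concern.** A category named as a risk of special interest should have one definition that sites, coders and programmers apply alike. Here the narrative describes infections occurring with neutropenia, while the table accepts one coded term. An investigator who follows section 9.2 and records the diagnosis will often enter pneumonia or sepsis. If Table 9 is applied, that event falls outside the category even when it arose during neutropenia.

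For serious neutropenia the risk runs the other way. By its name, the cytopenia query is not limited to neutrophils, so serious anaemia or thrombocytopenia could be counted under a neutropenia label if the query were used.

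The stake is interpretive. Section 2.3 names febrile neutropenia and neutropenia as eribulin's most common serious reactions, so whether adding balixafortide worsens their infectious consequences is a central safety question. The neutropenic-infection category is the planned output that links infection to neutropenia.

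**Working it through.** **Definitions side by side**

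| Source | Serious neutropenia | Infection |
|---|---|---|
| Protocol 2.6 | neutropenia | infections linked to neutropenia |
| Protocol 9.1, text | serious events | serious infection, no link to neutropenia stated |
| Table 9, AEPI half | cytopenia query 20000027 | one preferred term |
| Table 9, AESI half | reported events, no query | the same preferred term |
| SAP 9.1.8 | investigator flag | investigator flag |

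The rows do not agree, and no sentence says which prevails. Table 9 gives thrombocytopenia its own cell-line query (20000031, narrow), so the protocol does use cell-specific queries elsewhere.

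**Which outputs are exposed**

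SAP 9.1.8 plans these category-level outputs for serious neutropenia: maximum severity, onset by cycle and day, time spent in the event, and time to onset. If the cytopenia query fed them, a mixture of cell lines would not be visible. However, the SAP summarizes serious neutropenia as an AESI, and that row of Table 9 has no query. Exposure therefore depends on an unstated choice.

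**Display floor**

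Inputs: at least 4 patients and more than 1% of the Safety population (SAP 9.1.8); planned N of 384 overall, 192 per arm, and 320 in 3rd line+. I take the Safety population as the planned N, which is its upper bound.

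Floor = max(4, floor(0.01 × N) + 1).

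- N = 384: 1% is 3.84, so the floor is 4.
- N = 320: 1% is 3.2, so the floor is 4.
- The 1% condition raises the floor only from N = 400, where it becomes 5.

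The most the rule can withhold is therefore 3 patients over both arms: 3/384 = 0.78% (exact 95% CI 0.16% to 2.27%). If all 3 were in one arm, 3/192 = 1.56% (0.32% to 4.50%), and 3 versus 0 gives a two-sided Fisher p of 0.25.

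**How often the table would be filled**

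The documents give no rate for neutropenic infection, so the pooled rates p below are assumptions. P(filled) = 1 − Σ (k = 0 to 3) C(N,k) p^k (1 − p)^(N−k).

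| Assumed p | N = 384 | N = 320 |
|---|---|---|
| 0.5% | 0.13 | 0.08 |
| 1% | 0.54 | 0.40 |
| 2% | 0.95 | 0.88 |
| 5% | about 1.00 | about 1.00 |

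The two problems compound: a one-term definition lowers the count, and a lower count makes an empty table more likely. The matching severity summaries for serious neutropenia and febrile neutropenia in SAP 9.1.8 carry no such floor.

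**The case against.** The strongest reply is that Table 9 may not drive the counts at all. Under SAP 9.1.8 the investigator flags the event, so a pneumonia during neutropenia can be flagged as a neutropenic infection, and serious anaemia enters the neutropenia category only if someone flags it so. This stands as a limit on the effect. It does not remove the conflict, because the SAP never relates the flag to Table 9 and so adds one more unreconciled definition.

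A reader might infer that the main haematological risks are mismeasured. The documents do not support that. Febrile neutropenia and thrombocytopenia have their own categories, CTCAE shift tables are planned where grades are derivable, and pneumonia or sepsis would appear by arm under its own term.

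A reader might also infer that severe neutropenic infections would go ungraded. They would not. SAP 9.1.1 plans tables by preferred term and grade, Grade 3 or higher, Grade 4, serious and fatal events, plus listings, all with no minimum count.

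Nor does the 25% or higher frequency of anaemia in Protocol section 2.3 size any dilution of the neutropenia row. It covers adverse reactions in general, the row covers serious ones, and the same section names febrile neutropenia and neutropenia as the most common serious reactions.

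Section 9.2 prefers a diagnosis where possible; it does not bar recording neutropenic infection as that diagnosis. What remains is that the general tables show infections unlinked to neutropenia, so they do not fully replace the category.

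**Conclusion.** The definitional conflict holds; its reach is limited. Table 9 gives serious neutropenia two definitions under one label and narrows neutropenic infection to one term, against wider wording in sections 2.6 and 9.1. The SAP substitutes a flag without saying how it relates to either. It also conditions one severity table on a count, which does not fit its own section 12.

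The effect is on category-level outputs. Individual terms and grades remain available, and the display rule touches at most 3 patients at N = 384.

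Three assumptions carry this: the Safety population is close to the planned N; the cytopenia query is read from its name, since its contents are not in the documents; and the misses from the single term arise only if Table 9 is applied as written. No figure for the number of missed infections can be given.

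**What to change.** 1. Use one neutrophil-specific term list for serious neutropenia in both halves of Table 9.
2. Define neutropenic infection as the existing preferred term plus any event in the Infections and infestations class that starts during a recorded neutropenia adverse event, or with a concurrent low ANC where one was measured, at a threshold fixed in advance. Align sections 2.6 and 9.1 with it.
3. State whether the eCRF flag or the coded definition governs the counts.
4. Delete the 4-patient and 1% condition, and reconcile SAP 9.1.8 with section 12 on grade.

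The cost is wording in Table 9 and the SAP plus one derivation. The ANC part will be incomplete. Scheduled bloods fall on Days 1 and 8 (combination) or Days 2 and 9 (monotherapy), while section 9.2.6.4 reports a mean time to nadir of 13 days with eribulin; counted from the start of a cycle, that falls when no test is scheduled. The adverse event part should therefore carry the definition, and the report should state how often ANC was missing at infection onset.

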9.2 Adverse Events

All observed or volunteered AEs regardless of treatment group or suspected causal relationship to the study drug(s) must be reported as described in the following sections.

For all AEs, the Investigator must pursue and obtain information adequate both to determine the outcome of the AE, and to assess whether it meets the criteria for classification as a SAE requiring immediate notification to the Sponsor. Where possible, a diagnosis rather than a list of symptoms should be recorded. If a diagnosis has not been made, then each symptom should be listed individually. For all AEs, sufficient information should be obtained by the Investigator to determine the causality of the AE. The Investigator is required to assess causality. Follow-up by the Investigator may be required until the event or its sequelae resolve or stabilize at a level acceptable to the Investigator, and the Sponsor concurs with that assessment.

If a patient opts to discontinue from the treatment phase because of an unacceptable AE, "Withdrawal of Consent" must not be the reason for discontinuation, rather, the reason for discontinuation must be recorded as "Unacceptable Toxicity". Details of the AE leading to the patient's withdrawal of consent and the action taken must be completed on the AE CRF. AEs must be reported in accordance with the reporting requirements defined in Section 9.2.5.

